The exclusion criteria will be as follows: infant over 6 months of age, infant with intracranial pathology or a chronic respiratory disease that causes hypercapnia, parental refusal and surgical emergency.

✓ Anticipated benefits for participants.

The Doppler and cerebral oxygen saturation measurements are noninvasive and painless. The measurements will be made at different CO_2 levels within a range usually observed during general anesthesia in infants (9). In our study, we will vary the CO_2 in the direction of optimizing cerebral perfusion. (Example below with transcranial Doppler: diastolic velocity zero after intubation, and normalization after correcting the MAP and CO_2).

5. Statistical analysis

We will analyze the impact of changes in CO_2 on cerebral oxygen saturation and velocities. The Spearman coefficient of correlation will be used to study the correlations between the cerebral perfusion parameters (cerebral velocities and rSO_2c) and EtCO_2 . An ANOVA will be performed to determine the significant differences in rSO_2c and cerebral velocities according to EtCO_2 .

A change in EtCO_2 of +10 mm Hg could result in a relative increase in rSO_2c of +10%. Therefore, with a mean standard deviation of rSO_2c of 13% observed in the previous studies, we calculate the necessary number of subjects to be 36 (alpha risk = 5%; beta risk = 90%). To ensure that we will be able to analyze 36 patients, we hope to include 60 patients in the study. An interim analysis of the results will be performed after 20 patients have been included.

6. Timetable and funding

For the number of patients to be included ($n=60$), based on the volume of activity in the CHU Sainte Justine's surgical suite, we estimate that the duration of the study will need to be 18 months (3 to 5 patients a month).

The company Covidien is lending the cerebral oxygen saturation monitor and is providing the 60

sensors needed for the study. We will use the Department of Anesthesiology's sonograph.

Patient recruitment, parent explanations and the signing of the consent forms will be looked after by the anesthesiologist/principal investigator.

7. *References*

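### Does the interim analysis after 20 inclusions break the 5% alpha on which the sample size rests?

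*Protocol*

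**What the plan says.** Protocol section 5 (Statistical analysis) plans Spearman correlations between the perfusion measures and EtCO2, and adds: "An ANOVA will be performed to determine the significant differences in rSO_2c and cerebral velocities according to EtCO_2".

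The sample size rests on a 10 mm Hg rise in EtCO2 that "could result in a relative increase in rSO_2c of +10" per cent, "with a mean standard deviation of rSO_2c of 13% observed in the previous studies". From this, "we calculate the necessary number of subjects to be 36", with the risks printed as "alpha risk = 5%; beta risk = 90" per cent. The team aims for 60 inclusions so that 36 can be analysed. The section closes with: "An interim analysis of the results will be performed after 20 patients have been included".

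Section 6 (Timetable and funding) bases the 18-month duration and the supply of sensors on 60 patients. Neither section mentions stopping early, an interim significance level or a claim based on the first 20 infants.

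**The concern.** The interim is described as an analysis of results, and the only analyses that section 5 describes are tests on outcomes. A natural reading is therefore an early test of the CO2 effect, not a check on recruitment or data quality. The sample size spends the whole 5% at one analysis, with nothing visibly set aside for a first look.

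If the team tested at 5% after 20 patients, and could stop or report an effect on that basis, then tested again at 5% at the end, the chance of a false positive on a given endpoint would exceed the 5% used in planning. A claim that EtCO2 changes cerebral oxygenation would then rest on weaker evidence than its p-value suggests.

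**Working it through.** **Inputs.** From section 5: difference 10, SD 13, alpha 5%, 36 analysable, 60 inclusions, interim at 20 inclusions. Two assumptions are needed. Alpha is taken as two-sided, which the protocol does not say. The printed beta risk of 90% is taken to mean 90% power. Of the readings tried, this is the one that gives 36.

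**Step 1: reproduce 36.** With the two-independent-means formula:

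n = 2 × SD² × (z₀.₉₇₅ + z₀.₉₀)² / difference² = 2 × 13² × (1.960 + 1.282)² / 10² = 3.38 × 10.507 = 35.5, rounded up to 36.

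Other readings do not fit: one-sided alpha gives 29, 80% power gives 27, and a paired comparison with SD of differences 13 gives 18. So 36 does use the full 5% once. (It is a per-group number for independent groups, while each infant is measured repeatedly. That is a separate matter and does not enter the calculation below, which depends only on the ratio of the two sample sizes.)

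**Step 2: two unadjusted looks.** Under no effect, the interim and final z statistics are bivariate normal with correlation √(n₁/n₂). If either look can count, the overall error is 1 − P(|Z₁| < 1.96 and |Z₂| < 1.96).

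| Interim then final | n₁/n₂ | Overall error |
|---|---|---|
| 20 then 36 | 0.556 | 8.1% |
| 20 then 60 | 0.333 | 8.8% |
| 12 then 36 | 0.333 | 8.8% |

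The third row takes 20 × 36/60 = 12 analysable infants at the look. Simulated one-sample t-tests gave 8.2% (20 then 36) and 8.8% (20 then 60). With one-sided 5% looks the range is 7.8% to 8.5%.

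**Step 3: the same look under other rules.**

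- The look cannot stop the study or support a claim: 5.0%.
- Stopping allowed only at p<0.001, final test at 5%: 5.02% (20 then 36) or 5.05% (20 then 60).
- O'Brien-Fleming type boundary, exactly 5% overall: 0.0077 then 0.047 (final at 36), or 0.0007 then 0.0497 (final at 60).
- Equal levels at both looks (Pocock type), exactly 5% overall: about 0.030 (final at 36) or 0.028 (final at 60).

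**Step 4: does 36 rule out a controlled interim?** Put the O'Brien-Fleming final critical values into the formula of step 1:

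- Final value 1.985: 3.38 × (1.985 + 1.282)² = 36.1.
- Final value 1.962: 3.38 × (1.962 + 1.282)² = 35.6.

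Against 35.5, the difference is less than one patient. A calculation at the full 5% therefore shows only that no large adjustment, such as Pocock's, was built in. It does not show that the interim is mishandled.

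**Step 5: compare with the text.** The 8% to 9% requires an unadjusted 5% test at the interim and a consequence attached to it. Section 5 states neither. Following the protocol as written, the team looks after 20, continues towards 60 and tests once at the end, with error 5.0% per endpoint.

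**The case for a change.** The best case for a change is that the ambiguity is real and cheap to remove. The sentence speaks of results without restricting their use. The final size is loose: 36 are needed, 60 are only hoped for, and stopping anywhere between would look compliant. The principal investigator recruits the patients, and the protocol describes nobody separate from the study team who would see the interim data. Several outcomes are tested, so the per-endpoint figures do not overstate the overall risk.

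Much of this stands. The text does not exclude an informal early stop, and the 8% to 9% is correct for the case described. But it shows only that the protocol does not forbid misuse, not that it plans any. The purpose, boundary and alpha of an interim look are commonly set in the statistical analysis plan, which is not at hand. The word results need not mean hypothesis tests either. With an SD borrowed from previous studies and an expected yield of 36 out of 60, a descriptive look at spread and completeness fits the sentence equally well. The number of outcomes is a separate multiplicity question. In a study that tests oxygen saturation and several velocities, 5% per endpoint would not be a study-wide error rate with or without an interim.

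**Conclusion.** The concern does not call for a change. The protocol commits to a look at 20 patients and to a sample size calculated at 5%, and the two do not contradict each other. The error stays at 5.0% if the look carries no stopping or claim, and at about 5% if it carries a strict boundary. It reaches 8.1% to 8.8% for one endpoint only under an unadjusted 5% interim test that can end the study or support a claim, and the protocol does not state that combination.

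What remains is an unstated purpose for the look. Analysts can settle this in the analysis plan before the data are seen, with no extra patients and no revision of the figure of 36. The conclusion assumes that the final test is made once at a two-sided 5%, and that no early claim rests on the first 20 infants without a boundary. If a report showed that recruitment ended on a 5% result at the interim, the figures in the table would apply.
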